7.2.1 Focused Physical Examination (FPE)

At the time points indicated in the Schedule of Assessments ([Table 2](#)), the investigator or designee will perform a FPE of the subject that includes the face, head, and neck. Further details are provided in [Appendix 7](#).

Post-baseline, the signs and symptoms will also be monitored via FPE of face, head, and neck to evaluate local effect of toxin. In addition, a general physical examination to evaluate the remote spread events will be conducted. The list of remote spread of toxin events is considered while doing clinical evaluations based on subject's symptoms and signs ([Appendix 8](#)). Directed questioning and examination will then be performed as appropriate.

The investigator may choose to investigate any other sign that he/she observes during the physical examination. Clinically significant abnormalities noted pre-injection, i.e., at the screening/baseline visits, should be recorded as medical history and assessed as to whether the abnormalities affect subject eligibility. Clinically significant abnormalities noted post-injection should be recorded as AEs.

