7.2.4.1 Definitions

7.2.4.1.1 Adverse Events

According to International Council for Harmonisation (ICH) E2A,¹⁵ an AE is any untoward medical occurrence in a patient or a clinical investigation subject administered a pharmaceutical product and which does not necessarily have a causal relationship with this treatment. An AE can therefore be any unfavorable and unintended sign (including an abnormal laboratory finding), symptom, or disease temporally associated with the use of a medicinal (investigational) product, whether or not related to the medicinal (investigational) product.

Thus, any new sign, symptom or disease, or any clinically significant worsening of an existing sign, symptom or disease (including new episodes of a chronic disease [e.g., hay fever, allergy]) compared to the condition at the first visit, should be considered as an AE. Lack of efficacy is not considered as an AE.

Notes:

- There should be an attempt to report a diagnosis rather than the signs, symptoms or abnormal laboratory values associated with the report of an AE. However, a diagnosis should be reported only if, in the investigator's judgment, it is relatively certain. Otherwise, symptoms, signs, or laboratory values should be used to describe the AE.
- Pregnancy is not to be considered as an AE; however, is an important medical event that must be monitored as described in Section 7.2.4.2.3.

 EST. 1981	Title 43QM2106 Clinical Study Protocol – QM1114 – GL	Doc id MA-49290
---	--	---------------------------

- The effects of all BoNT products may spread from the area of injection to produce symptoms consistent with BoNT effects. These symptoms have been reported hours to weeks after injection. Remote spread of toxin that affects swallowing and breathing can be life threatening, and there have been reports of death. The risk of symptoms is increased in subjects who have underlying conditions (e.g. disorders of the neuromuscular junction) that would predispose them to these symptoms. BoNT is contraindicated in individuals with known hypersensitivity to any BoNT preparation or to any of the components in the formulation.

7.2.4.1.2 *Treatment Emergent Adverse Event*

A TEAE is an event that emerges during or after treatment, having been absent pre-treatment, or worsens relative to the pre-treatment state.

7.2.4.1.3 *Serious Adverse Events*

A SAE is any untoward medical occurrence that at any dose:

- Results in death,
- Is life-threatening,

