Severity is a clinical determination of the intensity of an AE and not the severity of a disease.

The investigator is to classify the intensity of AEs using the following definitions as a guideline. For this classification, the investigator will take into account the possible range of the intensity of the event and report the grade of intensity which is the most appropriate according to his/her medical judgment.

Mild Awareness of signs or symptom, but easily tolerated.

Moderate Discomfort, enough to cause interference with usual activity.

Severe Incapacitating with inability to work or perform usual activity.

7.2.4.1.7 *Relationship to the Study Product and/or Clinical Study Procedure*

The investigator is to determine whether there is a reasonable causal relationship between the occurrence of the AE and exposure to the study product and/or clinical study procedure.

Medical judgment should be used to determine the relationship, considering all relevant factors including the pattern of reaction, temporal relationships, relevant medical history, and confounding factors such as co-medication or concurrent diseases.

 EST. 1981	Title 43QM2106 Clinical Study Protocol – QM1114 – GL	Doc id MA-49290
---	--	---------------------------

The expression “reasonable causal relationship” is meant to convey in general that there are facts or arguments to suggest a causal relationship (ICH E2A, Section IIIA 1).

The relationship assessment for an AE is to be completed using the following definitions as a guideline:

Reasonable Possibility: According to the reporting investigator, there is a reasonable possibility (i.e., suggestive evidence or arguments) that there is a causal relationship irrespective of the dose administered between:

- The study product (active or placebo) and the AE.
- The clinical study protocol procedure (e.g., bruising or marks from blood draws, injection related trauma, etc.) and the AE.

A two-point scale (Yes or No response) shall be used for the causality assessment. The investigator shall be asked to indicate a response to each of the following questions in the eCRF:

- “Do you consider that there is a reasonable possibility that the event may have been caused by the study product?”, and
- “Do you consider that there is a reasonable possibility that the event may have been caused by the study product injection procedure?”

If any of these questions is answered Yes, the AE is considered related.

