9.1.3.1 Safety Analysis

All treatment related TEAEs by maximum intensity, treatment unrelated TEAEs by maximum intensity, treatment emergent SAEs by causality and maximum intensity, and action taken of treatment related TEAEs will be summarized by system organ class (SOC) and preferred term (PT) including number of subjects with at least one event, percentages, and number of events. All related TEAEs will also be summarized by time to onset and duration. In addition, a short summary of the analysis of TEAEs will be provided. AEs occurring before treatment will only be provided in subject data listings.

Data for vital signs will be summarized by descriptive statistics with the value at each visit as well as the change from baseline. The number and percentage of subjects with normal/abnormal results in physical examination will be presented by visit and treatment. A shift table will be created to present any change from baseline in normal/abnormal results in physical examination across the study visits for each treatment group. The results of the urine pregnancy tests will be listed.

All AEs will be monitored by the Sponsor to determine if they meet the criteria of remote spread of effect of the toxin or hypersensitivity. A list of preferred terms for these types of events will be referenced to in the DMP and will be further analyzed to determine if there is a plausible possibility that they represent remote spread of toxin or hypersensitivity. In order to perform the analysis, variables including alternative etiology (medical history, concomitant medication, or diagnosis which could account for the symptoms), location of QM1114-DP administration, and temporal relationship to QM1114-DP administration will be considered by the Sponsor.

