Appendix 7 Focused Physical Examination Form Example

Not done

Provide details: _____

General Health Assessment: Complete at Screening, Baseline (prior to treatment), and all post-treatment visits.

Question the subject about their general health (general wellbeing/ bodily functions, e.g., arms, legs, stomach/ bladder/ bowel, also refer to the list of Adverse Events Potentially Suggestive of Distant Spread of Toxin ([Appendix 8](#)). Clinically significant abnormalities noted pre-injection should be recorded as medical history and Investigator should confirm if any abnormalities affect subject eligibility. Clinically significant abnormalities noted post-injection should be documented as AEs.

Next, proceed to the Focused Physical Examination (Part 1 and 2) as indicated below.

Part 1: Complete at Screening, Baseline (prior to treatment), and all post-treatment visits.

Please perform a targeted examination of the face, head, and neck recording abnormalities and assess clinical significance.

Part 1 Examination	Normal	Abnormal (provide details)
Eyelid position		 Clinically Significant  Not Clinically Significant
Eyebrow position		 Clinically Significant  Not Clinically Significant
Vision abnormalities (not refractive errors)		 Clinically Significant  Not Clinically Significant
Throat function (e.g., swallowing/drink water)		 Clinically Significant  Not Clinically Significant
Ability to talk and chew		 Clinically Significant  Not Clinically Significant
Ability to stick out and move tongue		 Clinically Significant  Not Clinically Significant
Ability to lift shoulders		 Clinically Significant  Not Clinically Significant

Investigator Signature

Date

 EST. 1981	Title 43QM2106 Clinical Study Protocol – QM1114 – GL	Doc id MA-49290
---	--	---------------------------

PART 2: Complete at all post-treatment visits.

Not done Provide details: _____

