After questioning the subject about their general health and performing Part 1, determine if there are any **clinically significant abnormalities** that may suggest local or remote spread of toxin effect.

- Local Spread of Toxin Effect refers to effects in areas adjacent to the treatment area (e.g., lower frontalis, periorbital area, medial part of temporalis).
- Remote Spread of Toxin Effect refers to effects in other body parts, not adjacent to the treatment area, when effect can only be attributed to the toxin and there is no other medically sound cause.
- Determine if the event is clinically significant (i.e., would affect subject safety, confound the study data, or requires medical treatment) and document on the source document.

Please refer to the list of remote spread of toxin events ([Appendix 8](#)) while doing clinical evaluations based on subject's symptoms and signs. Directed questioning and examination will then be performed as appropriate. If yes, please describe.

Part 2 Examination	No	Yes* (provide details)
Targeted Physical Examination of Face and Neck to Evaluate Local Spread of Toxin Effect 
 • Local spread of toxin effect event(s) observed? 		
General Physical Examination to Evaluate the Remote Spread of Toxin Effect 
 • Remote spread of toxin effect event(s) observed? 		

* Clinically significant abnormalities should be documented as AE.

Additional comments for Focused Physical Exam:

Investigator Signature

Date

2022-03-21 13:08

Effective date:

Effective

Version: 3.0

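### The protocol has two rules for when a new examination sign becomes an AE, so mild lid, brow or spread signs can be missing from the TEAE tables and the spread review

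*Protocol*

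**What the plan says.** The AE definition in protocol section 7.2.4.1.1 reads: "Thus, any new sign, symptom or disease, or any clinically significant worsening of an existing sign, symptom or disease". Clinical significance qualifies the worsening of an existing sign, not the appearance of a new one. Section 7.2.4.1.6 provides a Mild grade: "Awareness of signs or symptom, but easily tolerated".

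For examination findings, section 7.2.1 says: "Clinically significant abnormalities noted post-injection should be recorded as AEs". It does not define the term. Appendix 7, an example form, has two parts:

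- Part 1 lists items such as eyelid and eyebrow position and asks for "recording abnormalities and assess clinical significance". Each abnormal item is ticked as clinically significant or not. The term is not defined there.
- Part 2 covers local and remote spread. It instructs: "Determine if the event is clinically significant (i.e., would affect subject safety, confound the study data, or requires medical treatment". Its footnote says: "Clinically significant abnormalities should be documented as AE".

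The first safety endpoint in section 2.1.4 is the incidence and severity of TEAEs. Examination findings are a separate endpoint in the same list. The TEAE tables in SAP 2.5.2 use recorded AEs. The sponsor's remote-spread and hypersensitivity review (protocol 9.1.3.1, SAP 1.5.1) also starts from recorded AEs. Protocol 9.1.3.1 and SAP 2.5.4 plan normal/abnormal counts by visit and treatment, and shift tables from baseline, for the physical examination.

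**The concern.** The two rules give different answers for one kind of finding: a new sign that the examiner sees, that is mild, and that needs no treatment. Section 7.2.4.1.1 makes it an AE. Section 7.2.1 and Appendix 7 let a site tick it as abnormal but not clinically significant and stop there.

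Such findings fall within the local risk that the protocol itself names. Section 6.1.7.1 gives eyelid ptosis as its example of a regional toxin effect. Exclusion criterion 10 bars subjects with a history or presence of eyelid or brow ptosis, so a lid or brow abnormality after injection will usually be a new sign, which is where the rules diverge.

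At stake is whether the TEAE rate means the same thing at every site. SAP 2.5.2.1 repeats the related-TEAE table by site, so sites that follow different sections could differ there because of recording alone. A sign that is never recorded as an AE also cannot enter the sponsor's spread review.

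**Working it through.** The plan states no figure on this point, so there is nothing to reproduce. The main check is to take one case through each rule: a new, slight, untreated change in eyelid position, noted by the examiner and not mentioned by the subject.

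| Step | Section 7.2.4.1.1 with 7.2.4.1.6 | Section 7.2.1 with Appendix 7 |
|---|---|---|
| Is it a new sign? | Yes | Yes |
| Is clinical significance required? | No | Yes, to trigger the stated AE instruction |
| Result | AE, graded Mild | Part 1: abnormal, not clinically significant; no instruction to record an AE |
| TEAE tables (SAP 2.5.2) | Counted | Not counted |
| Sponsor's spread review (protocol 9.1.3.1, SAP 1.5.1) | Screened | Not reached |
| Normal/abnormal and shift tables (SAP 2.5.4) | Counted | Counted |

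The last row is the same under both rules, but it does not replace the TEAE row. SAP 1.5.2 says that clinically significant findings will be assessed, yet SAP 2.5.4 specifies only normal/abnormal, with no split by item or by clinical significance. Those tables also carry no severity grade, causality or duration.

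Part 2 has a further filter. Before its yes/no boxes it asks whether there are clinically significant abnormalities that may suggest spread, so a mild effect may be answered No there too. Neither document names a summary output for the Part 2 answers.

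**Size, by illustration.** The active arm has n = 90 (protocol section 3). The true rate p of such signs and the share s that never become AEs are assumptions, because the documents give neither.

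- Expected subjects counted = 90 × p × (1 − s)
- Chance that the AE table shows at least one = 1 − (1 − p(1 − s))^90

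| p | s = 0 | s = 50% | s = 75% |
|---|---|---|---|
| 1% | 0.9; 59.5% | 0.45; 36.3% | 0.225; 20.2% |
| 3% | 2.7; 93.6% | 1.35; 74.3% | 0.675; 49.2% |
| 5% | 4.5; 99.0% | 2.25; 89.8% | 1.125; 67.8% |

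For example, p = 3% and s = 50% gives 90 × 0.03 × 0.5 = 1.35 and 1 − 0.985^90 = 74.3%.

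**The case against.** The strongest reply is that the examination is only one route to an AE. No passage says that a finding without clinical significance is not an AE; that is an inference from the instruction given. Sections 7.2.4 and 7.2.4.2.1 still require all AEs to be reported, and an open question is asked at each post-enrollment visit. This stands for what a subject notices and mentions. It does not settle the case of a sign that only the examiner sees.

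A second reply is that the narrow definition sits in Part 2 of an example form, while the lid and brow boxes are in Part 1, where the term is undefined. The limb about confounding the data could also be read to cover a lid or brow change. This stands too, but it means that the threshold is left to each site.

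Third, both blinded arms use the same form and randomization is stratified by site, so uneven recording between sites does not by itself create a difference between arms. That is correct. If the same share s is missed in both arms, however, each rate and the difference between them are multiplied by (1 − s).

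A reader might infer three stronger points, which the documents do not support:

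- **That mild lid and brow signs vanish from all safety tables.** They do not. Part 1 records them as abnormal whatever their significance, and they reach the normal/abnormal and shift tables. Absence from every summary is plausible only for spread signs with no Part 1 item, such as those in the limbs, bladder or bowel.
- **That the form contradicts the protocol body.** Section 7.2.1 is in the body and has the same clinical-significance wording. The tension is between 7.2.1 with Appendix 7 and 7.2.4.1.1.
- **That the two remote-spread criteria conflict.** The form accepts remote spread "when effect can only be attributed to the toxin and there is no other medically sound cause", whereas the sponsor's review asks "to determine if there is a plausible possibility that they represent remote spread of toxin or hypersensitivity". These are separate steps. SAP 1.5.1 cross-references the sponsor's determination with investigator-reported events and has all AEs adjudicated before unblinding. The strict wording on the form does not narrow the sponsor's search among recorded AEs.

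**Conclusion.** The inconsistency is real and concerns the first listed safety endpoint. For a new, mild, untreated sign that the examiner notes and the subject does not report, sections 7.2.1 and 7.2.4.1.1 lead to different AE records. Such a sign can be absent from the TEAE incidence and severity tables and from the spread review. The planned examination tables keep Part 1 abnormalities, but not in a form that shows how many were lid or brow changes or how many were judged not clinically significant.

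The size cannot be fixed from the documents. The illustration shows only that, at assumed true rates of 1% to 5%, losing half or three quarters of events would noticeably lower the count in 90 subjects. It does not show that such a loss will occur. The primary efficacy analysis is not affected. The point merits a change before database lock because it is cheap and bears on a stated endpoint.

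**What to change.** Reconcile sections 7.2.1 and 7.2.4.1.1 and both parts of Appendix 7 so that one stated rule decides when a new post-injection examination finding is recorded as an AE. Which rule to adopt is the sponsor's decision and is not chosen here. The text should also say whether the Part 2 yes/no answers are limited to clinically significant findings.

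In SAP 2.5.4, present the planned normal/abnormal and shift tables by Part 1 item, with abnormal findings split by clinical significance. Add the Part 2 local-spread and remote-spread answers by arm and visit, regardless of AE status.

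The cost is protocol and form wording plus one or two tables. The form already collects the data. If the Part 2 answers are held only in source documents, which the text does not settle, they would also need a field in the eCRF. The reported rate of mild local events may rise.

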1.1 Background

1.1.1 Study design

This is a phase 3, randomized, double-blind, placebo-controlled study to assess the efficacy and safety of QM1114-DP in the treatment of moderate to severe glabellar lines (GL).

Eligible subjects will be randomized to receive a single treatment at baseline of 50 units (U) of QM1114-DP or placebo in the glabellar region. Following treatment at baseline, subjects will be monitored for safety and efficacy according to the Schedule of Assessments for 12 months.

1.1.2 Number of subjects and randomization

The study will screen approximately 134 male and female adults, 18 years of age or older, with moderate to severe glabellar lines at maximum frown and previous treatments with BoNT-A products within the 3 years prior to screening visit. A total of approximately 120 subjects will be randomized and enrolled at least 5 study sites. Following the screening process, eligible subjects will be randomized at the baseline visit (Day 0) in a 3:1 ratio to QM1114-DP or placebo, stratified by site.

1.2 Study Objectives

The objective of the study is to evaluate the aesthetic improvement and onset of QM1114-DP treatment effect in subjects with moderate to severe GL.

1.2.1 Primary efficacy objective

The primary efficacy objective of the study is to demonstrate superiority in aesthetic improvement following a single dose of 50 units of QM1114-DP compared to placebo for the treatment of moderate to severe GL using the Global Aesthetic Improvement Scale (GAIS) (described in [Section 1.3.1](#)) at maximum frown at Month 1.

1.2.2 Secondary efficacy objectives

The secondary efficacy objectives of the study as assessed using the endpoints in [Section 1.4.2](#) are:

- To evaluate onset of treatment effect following a single dose of 50 units of QM1114-DP and placebo as assessed by the subject using the diary card on Days 0 through 7 post-treatment (as described in [Section 1.3.2](#)).

- To evaluate aesthetic improvement following a single dose of 50 units of QM1114-DP and placebo as assessed by the subject using the GAIS at maximum frown at all applicable time points ([Section 1.3.1](#)).

CCI

1.2.4 Safety objective

The safety objective of the study is to evaluate the safety of a single dose of 50 units of QM1114-DP and placebo in the treatment of moderate to severe GL.

1.3 Efficacy assessment

For all assessments, baseline will be defined as the observation that is closest to but prior to study injection on Day 0. Likewise, in general change from baseline (Δ) will be calculated as the value at a given time point, X , minus the baseline value:

$$\Delta = X \text{ Value} - \text{Baseline (Day 0) Value}$$

1.3.1 Global Aesthetic Improvement Scale (GAIS)

The GAIS consists of seven ratings used to assess the aesthetic improvement of the GL at maximum frown relative to pre-treatment appearance. Subjects will be asked:

- *“How would you rate the change in appearance of your glabellar lines (lines between your eyebrows) at maximum frown compared with immediately before the injection?”*

Subjects will be instructed to select the one rating, using the below categorical scale ([Table 1](#)), that best describes the degree to which the appearance of their GLs at maximum frown has changed relative to baseline. Ratings will also be recoded with numeric values 0-6 (as seen in Table 1). The subject may review the baseline photograph to aid in the assessment.

Subjects will rate the global aesthetic improvement of their GL at maximum frown, relative to their pre-treatment appearance, at all post-treatment visits.

Table 1. Global Aesthetic Improvement Scale

Recoded Value	Rating
0	Very Much Improved
1	Much Improved
2	Improved
3	No Change
4	Worse
5	Much Worse
6	Very Much Worse

A responder indicator will be created to identify subjects that experienced an improvement in aesthetic appearance of their GL at maximum frown. If at any given visit the subject selects ‘Improved’, ‘Much Improved’, or ‘Very Much Improved’ on the GAIS, the subject will be considered a Responder at that visit. The subject will be considered a Month 1 Responder only if they are a responder at the month 1 visit.

